11.5	DATA SAFETY MONITORING BOARD (DSMB).....	19
12	DATA COLLECTION AND MANAGEMENT PLAN.....	19
12.1	DATA COLLECTION.....	19
12.2	DATA HANDLING AND RECORD KEEPING.....	19
12.3	DATA TRANSMISSION FROM SPONSOR.....	20
12.4	STUDY MONITORING PLAN.....	20
13	RISKS AND BENEFITS.....	20
14	ETHICAL CONSIDERATIONS.....	21
14.1	SUBJECT CONSENT AND CONFIDENTIALITY.....	21
14.2	SUBJECT FINANCIAL RESPONSIBILITY AND STIPENDS.....	21
15	PUBLICATION PLAN.....	21
16	INTELLECTUAL PROPERTY AND PATENTS.....	22
17	LIST OF ABBREVIATIONS.....	22
18	BIBLIOGRAPHY.....	23

Study Summary

Title	BENEFITS OF MICROCOR (μ Cor™) IN AMBULATORY DECOMPENSATED HEART FAILURE
Short Title	BMAD HF
ZOLL Protocol Number	90D0182
Study Design	Prospective and Observational Study
Study Duration	The study duration will last an estimated 2.5 years with 1 year estimated for enrollment
Study Center(s)	30 to 50 centers (Multinational)
Primary Objective(s)	To identify correlations between μ Cor measurements (thoracic fluid index, respiration rate, cardiac rhythm, physical activity, and posture) with occurrences of heart failure related clinical events within 90 days of hospital discharge for acute decompensated heart failure.
Study Population	Subjects hospitalized for acute decompensated heart failure or subjects presenting to an outpatient clinic within 10 days post-hospital discharge for heart failure. All subjects require an additional heart failure event within the previous 6 months.
Intervention	
Subjects meeting the inclusion/exclusion criteria will wear the μCor for up to 90 days.
 
During the study, clinic follow up will occur every 30 days. For all subjects, each scheduled clinic visit will include assessment of cardiac symptoms and any relevant clinically actionable events.
 
The subject will be given a daily diary to track symptoms, unplanned hospital visits, medication changes, and all other heart failure related clinical events.
 
Weekly phone calls to the subject will be given throughout the duration of the study to remind the patient to use the subject diary and to collect and record heart failure related clinical events.
 
Subjects will be contacted six months and one year from initial enrollment to assess the vital status of the subject, any heart failure related clinical events since the end of μCor wear, and any health care utilization since the end of μCor wear.

Study Size	A total of 500 subjects
Reference therapy	NA

1 Introduction

This document is a protocol for a human research study. This study is to be conducted according to US and international standards of Good Clinical Practice (International Conference on Harmonization ICH E6), the Code of Federal Regulations Title 21 parts 803 and 812, and other applicable government regulations.

1.1 Background

Annually, over 1 million patients are hospitalized with a primary diagnosis of heart failure (HF) ¹. Despite improvement in outcomes with medical therapy, readmissions for acute decompensated HF are common and place a significant burden on the healthcare system. Therefore, strategies for outpatient monitoring and fluid management are needed to reduce HF hospitalizations. Rather than low cardiac output, the main reasons for rehospitalization are symptoms associated with pulmonary and systemic venous congestion due to elevated ventricular filling (end-diastolic) pressures ². Remote monitoring of these pressure changes in addition to its surrogate measures, such as intrathoracic impedance, lung fluid levels, systolic time intervals, or the presence of abnormal heart sounds, may help to prevent hospitalization by detecting early evidence of HF decompensation ^{3,4,5}. In addition, remote monitoring may lead to better access to care and coordination of services.

Given the anticipated importance of remote HF monitoring and fluid management, ZOLL has developed a novel radiofrequency (RF) based heart failure and arrhythmia management system (μ Cor Heart Failure and Arrhythmia Management System). Using the RF data, μ Cor provides an estimate of the thoracic impedance. In addition, the system records the electrocardiogram (ECG) through adhesive electrodes and respiration rate, activity, and posture through a tri-axial accelerometer. The purpose of this study is to correlate μ Cor readings with clinically actionable heart failure events during the ninety days after hospital discharge. In addition, the rate of occurrence of VT/VF episodes and arrhythmic death in patients with an LVEF greater than 35% will be observed.

1.2 Preclinical Data

In animal testing, μ Cor's noninvasively determined RF thoracic fluid content was compared with invasive thermodilution extravascular lung water measurements (PiCCO - Pulsion Medical Systems, Munich, Germany). Pulmonary edema was induced in 15 sheep by intravenous volume and pressure overload. μ Cor was placed on the left lateral torso of the sheep. The emitted and reflected RF signals are used by μ Cor to assess thoracic fluid. These readings were compared with the readings from the PiCCO device. Results of the study showed that all 15 sheep developed increases in left ventricular end diastolic pressure, and the onset of pulmonary congestion and edema. A consistent linear correlation ($r = 0.97$) between measurements of invasive lung water fluid and noninvasive thoracic fluid content was observed. μ Cor RF signals were able to detect dynamic accumulation of lung water in the range of 50-60 ml increments. The change in lung water needed to produce congestion was between 250-500 ml. The results of this study support the use of ZOLL's external RF sensor for high resolution and precise fluid monitoring.

1.3 Clinical Data to Date

A validation study was conducted in human subjects to compare μ Cor noninvasively-determined RF thoracic fluid content with invasive thermodilution extravascular lung water

measurements (PiCCO - Pulsion Medical Systems, Munich, Germany). 36 patients in critical care unit with a clinical indication for thermodilution based extravascular lung water monitoring were studied. μ Cor was placed on the patients left chest. Noninvasive thoracic fluid assessment was compared to the invasive extravascular lung water measurement every 30 minutes. Cardiac output, systolic and diastolic blood pressure, and heart rate were also measured. Results showed that the pooled correlation between measurements of invasive lung water fluid and noninvasive thoracic fluid content was excellent ($r = 0.86$). Also, increases in lung water of 90 ml could be detected by the RF signal. Furthermore, lung water change did not correlate to systolic blood pressure, diastolic blood pressure, cardiac output, and cardiac index (correlation range, $r = 0.12-0.54$). This study demonstrated accuracy and usability of this RF technology to support its use for high resolution fluid monitoring in patients.

1.4 Study Device

1.4.1 System Components

μ Cor consists of the following components:

- A) Patch
- B) Sensor
- C) Charger
- D) Data transmission device (Gateway)
- E) Server

Once activated, the wearable Sensor automatically acquires ECG, RF readings, heart rate, respiration rate, activity, and posture measurements. Data are automatically transmitted from the Sensor to the Data transmission device, and from there to the Server for analysis (see Fig. 1).

[figure not shown]

Figure 1: Data transmission of μ Cor

1.4.2 Patch

The Patch (Fig. 2) consists of a plastic frame intended for housing the Sensor, and two ECG electrodes on each side of the frame. The Patch is a single-use, disposable item.

[figure not shown]

Figure 2: Patch

1.4.3 Sensor

The Sensor (Fig. 3) is a battery powered unit that acquires data. The Sensor connects to the Patch via the snap-in clip and positioning tabs. Through the adhesive backing on the Patch, the device becomes wearable. The Sensor is not disposable and needs to be returned to ZOLL upon the completion of the study. A light indicator is located close to the center and serves to communicate the Sensor's status at different points of use. Note that the light indicator is visible only when lit.

[figure not shown]

Figure 3: Sensor's front view

1.4.4 Charger

A dedicated Charger (Fig 4) is supplied with the μ Cor System for recharging the Sensor and the Data Transmission Device. A blue light appears when the Charger is connected to an AC outlet.

Figure 4: Charger

1.4.5 Data transmission device (Gateway)

A Data Transmission Device or Gateway is responsible for sending data from the Sensor to the Server for data analysis. When the screen display is on, the gateway battery status is visible on the screen. Once the battery status is under a certain level, a short beeping sound will be made every few minutes until the battery is depleted or the Gateway is placed in the Charger.

[figure not shown]

Figure 5: Gateway

1.4.6 Server

The Server refers to the hardware and the processing software and resides in a remote cyber-secure location. The software analyzes the data received from the Sensor via the Gateway and processes the data into clinical values.

1.4.7 Device (Sensor +Patch) Placement Location

There are two locations for device (Sensor + Patch) placement: (1) along the left anterior axillary line in line with the nipple (side location) and (2) along the left mid-clavicular line, above the nipple and below clavicle.

[figure not shown]

Figure 6: Device (Sensor + Patch) placement location. Side location is the left anterior axillary position. Front location is the left mid-clavicular position.

2 Study Objectives

2.1 Primary Objective(s)

The following primary objectives will be evaluated during the wear period of the μ Cor device:

- 2.1.1 To identify correlations between μ Cor measurements (thoracic fluid index, cardiac rhythm, respiration rate, physical activity, and posture) with occurrences of heart failure related clinical events occurring within 90 days of hospital discharge for acute decompensated heart failure.

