During the Day 90 visit, the subject will be given the option to continue wearing the μ Cor for an additional 90 days. Furthermore, if the subject experienced a heart failure related clinical event within the initial 90 days of wear, the subject will be given the option of wearing the μ Cor for 30 days following the heart failure event. If the subject chooses additional wear time, weekly phone calls and monthly visits will be structured identical to that of the main study period. The μ Cor will be returned at end of use.

There will be a follow up at six months and one year post enrollment to document mortality data, heart failure related clinical events, and health care utilization data. A timeline visualization of the study procedure is shown in Figure 7.

[figure not shown]

Figure 7: Procedure Flow of BMAD Study

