3.3 Secondary Study Endpoints

The various secondary endpoints that will be evaluated during the entire study include:

- 3.3.1 Establishment of rate of occurrence of VT/VF episodes and arrhythmic death in patients.
- 3.3.2 Correlation between μ Cor measurements and patient reported symptoms
- 3.3.3 Frequency, timing, and severity of patient reported symptoms
- 3.3.4 Hospital readmission rate during the study period
- 3.3.5 Hospital readmission rate during previous 90 days prior to enrollment in study.
- 3.3.6 Cost-effectiveness data that supports a benefit in quality adjusted life years (QALY)
- 3.3.7 Mortality, heart failure related events, and health care utilization data at six months and one year post enrollment

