6.1.3 Screening definitions

An acute heart failure event requiring medical management is defined as a hospitalization, emergency room visit, observation unit visit, or unplanned clinic visit where medical management or treatment for HF related pulmonary congestion is administered.

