6.4 Long-term Clinical Outcome Assessment

The subject will receive a follow up phone call 6 months and 1 year from the enrollment date to assess for mortality status, heart failure related clinical events that have occurred since the end of μ Cor wear, and any health care utilization that has occurred since the end of μ Cor wear. A chart review will be performed during both of these calls as well. Subjects will answer mailed heart failure questionnaires and mail the questionnaires back to the site.

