8.1 Sample Size and Power Calculation

The sample size was chosen to answer the primary and secondary objectives. We expect a 50/50 distribution between patients enrolled with an LVEF less than 35% and an LVEF greater than 35%. After the 200th patient is enrolled, we will conduct an interim analysis to confirm the LVEF distribution.

The first 200 patients will generate a convenience sample of heart failure related clinical events. Assuming a 20% event rate within the first 30 days in patients with reduced LVEF, we estimate that we will observe at least 25-30 heart failure related events among patients with reduced EF through the length of the 90 day study period (accounting for not all patients reaching completion).

We believe that 25-30 heart failure related events will be enough events to draw meaningful correlations among μ Cor device measurements and heart failure related episodes.

Following the interim analysis, the additional 300 subjects will further generate heart failure related clinical events to answer the primary objective and be monitored for VT/VF arrhythmic events to answer the secondary objectives.

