8.3 Endpoint Assessment

8.3.1 Primary endpoint

The first primary endpoint will be assessed by the strength of the correlation between μ Cor device readings and heart failure related clinical events.

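### The primary correlation has no time at risk and no rule for death, so a fatal decompensation may be coded event-free, dropped or counted

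*Combined protocol and SAP*

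**What the plan says.** All references are to the combined protocol and SAP.

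- **Objective and window.** Section 2.1 opens: "The following primary objectives will be evaluated during the wear period of the" device. Objective 2.1.1 relates the readings "with occurrences of heart failure related clinical events occurring within 90 days of hospital discharge for acute decompensated heart failure". Wear is up to 90 days from fitting (3.1.1).
- **Analysis.** Section 8.3.1: "The first primary endpoint will be assessed by the strength of the correlation between" device readings and HF events. Section 8.4 adds only descriptive and qualitative summaries. No coefficient, model, unit of analysis, censoring rule or competing-event rule appears.
- **Event definition.** No outcome definition is given. The only HF event definition is in 6.1.3, under the screening definitions, for use in the inclusion criteria. There an acute event "is defined as a hospitalization, emergency room visit, observation unit visit, or unplanned clinic visit where medical management or treatment" for HF-related pulmonary congestion is given. Death is not listed.
- **Death.** Mortality stands beside HF events as a separate item in three places: the six-month and one-year contacts in 3.1.1 ("to document mortality data, heart failure related clinical events, and health care utilization data"), endpoint 3.3.7 ("Mortality, heart failure related events, and health care utilization data at six months and one year post enrollment"), and 6.4 ("to assess for mortality status, heart failure related clinical events that have occurred since the end of" wear). Cause of death falls under secondary objective 2.2.5.
- **Incomplete follow-up.** Section 8.1 describes its event count as "accounting for not all patients reaching completion". Section 8.6.3 imputes nothing and removes any subject with over half of the data missing.

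**The concern.** A plain correlation with whether an event occurred gives the same weight to a subject seen for 50 days without an event and one seen for 90. Clinic visits end when wear ends. Sections 6.2 and 6.6 also end the phone calls at that point, while 3.1.1 continues them, so it is unclear whether later events would be captured at all.

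Death is the sharpest case of truncated observation, and here it is linked to the outcome. Exclusion 4.2.2 removes only subjects expected to die within a year of non-cardiac disease, so cardiac deaths are foreseeable. A fatal decompensation is the most severe form of what the device is meant to detect. Placed among the non-events, it brings event-like readings into the comparison group. Removed, it takes out an informative case. With only 25-30 events expected from the first stage, a few such subjects are not negligible.

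**Working it through.** **1. The plan's own count.** Section 8.1 gives 200 subjects, a 50/50 LVEF split and 20% with an event by day 30 in reduced LVEF.
- Reduced-LVEF subjects: 200 × 0.5 = 100. Events by day 30: 100 × 0.20 = 20.
- Constant hazard to day 90: 100 × (1 − 0.8³) = 48.8.
- The stated 25-30 is then 25/48.8 = 51% to 30/48.8 = 61% of that figure.

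The count is attainable but cannot be confirmed, because the plan gives neither the attrition nor the event rate after day 30. The point does not depend on it.

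**2. What ignoring time at risk does.** Compare the same subject observed for 50 or for 90 days.
- Constant hazard: 1 − 0.8^(50/30) = 31% against 49%.
- If 25-30% is instead the full 90-day risk, with the 5-10 points after day 30 spread evenly: 20 + (5 to 10)/3 = 21.7-23.3% against 25-30%.

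Either way, part of the observed event status reflects length of observation.

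**3. Three codings of one fatal decompensation with no earlier HF contact.**
- *Event-free*, if the care contacts in 6.1.3 are borrowed as the outcome.
- *Dropped*, under 8.6.3.2. The rule does not define data. If it means wear days, the cut is 0.5 × 90 = 45 days: a death before day 45 is removed, while a death on day 50 (40/90 = 44% missing) stays in.
- *Counted*, because the outcome is undefined and cause of death is collected.

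**4. Size, on the reduced-LVEF basis of 8.1.** Assumptions, none from the documents: 5-10% die within 90 days; half of these have no earlier HF visit; all of that half are HF deaths with event-like readings.
- Subjects affected: 100 × (0.05 to 0.10) × 0.5 = 2.5-5.
- Relative to expected events: 2.5/30 = 8% to 5/25 = 20%.
- If counted: 27.5-35 events in place of 25-30.
- If not counted, share of true events lost: 2.5/32.5 = 8% to 5/30 = 17%.
- AUC under event-free coding = 0.75 − 0.25 × f, where f is the deaths as a share of the non-events. With 75 non-events: f = 2.5/75 gives 0.742 and f = 5/75 gives 0.733. With 70 non-events: 0.741 and 0.732.
- Correlation under event-free coding is multiplied by √[p_c(1 − p_t) / (p_t(1 − p_c))], where p_c is the coded and p_t the true event proportion. For 2.5% affected the factor is 0.94, and for 5% it is 0.88-0.89. A true r of 0.50 becomes 0.44-0.47. If only 1% are affected, the factor is 0.97-0.98.

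**5. Whole-cohort basis.** Section 8.7 can be read as 25-30 events among all 200. Then 5-10 deaths fall among 170-175 non-events: 0.75 − 0.25 × 5/175 = 0.743 and 0.75 − 0.25 × 10/170 = 0.735. The loss is again about 0.01-0.02.

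For scale, the 95% Fisher interval for r = 0.50 with 100 subjects is 0.34-0.63, wider than any shift above.

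**The case against.** The strongest reply is that no section codes a fatal decompensation as event-free. A reader might infer such a rule from the separate listing of mortality, but the documents do not support it as a rule. Section 6.1.3 serves screening. The visit questions and the diary are answered by the subject, so death could not appear in them. Endpoint 3.3.7 and section 6.4 concern six months and one year, not the primary window. A death in hospital or the emergency room after treatment for congestion would already meet the 6.1.3 wording. All of this stands. It leaves the coding open rather than settled.

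Second, the plan fixes no unit of analysis. A within-subject comparison of readings before events would also fit 2.1.1, and event-free subjects need not then form the comparison group. That is fair. A fatal decompensation that is not recognized as an event would still be lost as a case.

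Third, the effect is small, the death rates are assumed, and the study is observational with no stated test or success threshold. This stands too. A reader might reach a larger figure by placing the 5-10 deaths from all 200 subjects among the 75 reduced-LVEF non-events, but that mixes denominators. A reader might also suppose that the error is worst in low LVEF; the documents give no death rate by LVEF.

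Fourth, including HF death in the event is a choice of target. It is, but the plan has to make some choice, and at present it makes none.

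**Conclusion.** The point holds as a gap in the primary analysis: there is no outcome definition, no time at risk, and no rule for death or early end of wear. The three codings that the text allows lead to different analyses, and the choice could be made after the data are seen. Dilution follows only under event-free coding; exclusion instead loses severe cases.

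Under the assumed 5-10% mortality, half without an HF visit, about 2.5-5 of 100 reduced-LVEF subjects are affected, and an AUC of 0.75 would be seen as about 0.73-0.74. That loss is modest and would shrink with fewer such deaths or if some were not HF deaths. The missing time at risk matters whatever the death rate. The plan should be changed, mainly because the remedy is cheap and settles the matter in advance.

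**What to change.** In section 8.3.1:

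1. Define the primary event as the first HF related clinical event or HF death within the primary window, and list the care contacts that qualify. Name one window: 2.1 uses the wear period and 2.1.1 counts from discharge, while fitting may come up to 10 days after discharge.
2. Analyze it as time to event, with non-HF death as a competing event and censoring at withdrawal, end of wear or end of the window. Report reasons for stopping wear, since censoring there assumes that stopping is unrelated to an impending event.
3. State in 8.6.3.2 that subjects whose data end because of death are not removed, and say what data the rule counts.
4. Add one sensitivity analysis with death from any cause as an event.

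Reconcile 3.1.1 with 6.2 and 6.6 on phone calls after wear stops.

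**Cost.** Mostly wording, plus slightly more analysis. The one real addition is classifying cause of death for deaths inside the 90-day window: 2.2.5 already requires cause of death, but at six months and one year, and no procedure for deciding that a death was due to HF is described.

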2.2 Secondary Objective(s)

The specific secondary objectives that will be evaluated during the entire study include:

- 2.2.1 To identify the rate of occurrence of VT/VF and arrhythmic death in heart failure patients based on left ventricular ejection fractions (LVEF).
- 2.2.2 To identify correlations between μ Cor measurements (physiologic variables including thoracic impedance, cardiac rhythm, respiration rate,) and patient reported symptoms.
- 2.2.3 To identify the hospital admission rate of patients during the study period.
- 2.2.4 To identify the hospital admission rate of patients in the previous 90 days before enrollment into the study.

- 2.2.5 To define the mortality rate, cause of death, and health care utilization among patients six months and one year after enrollment into the study.

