3.1 General Design

3.1.1 Study Description

Subjects meeting the inclusion/exclusion criteria will wear μ Cor for up to 90 days from the day of fitting. 500 total patients will be enrolled. There will be an interim analysis when the 200th subject has finished the study to assess for distribution of patients with reduced and preserved LVEF. The first 200 subjects enrolled in the US will exclusively wear the device in the side position. The subsequent subjects in the US will follow an alternating pattern of front position and side position placement.

Subjects will be fitted with μ Cor during discharge of a heart failure related hospitalization or within a clinic visit that has occurred within 10 days of a heart failure related hospitalization. The μ Cor fitting will mark day 0 of the study. An LVEF measurement will be recorded during enrollment or within 30 days post enrollment if an LVEF measurement has not been recorded within 30 days prior to enrollment. An investigator assessment will be performed during all clinic visits. The assessment template is shown in Appendix A.

Subjects will be given a diary at enrollment that will ask them to rate their degree of specific symptoms of heart failure such as shortness of breath and fatigue as well as mark any heart failure related clinical events or medication changes that have occurred since the last entry. The subject diary is shown in Appendix A.

Study follow up visits will occur at day 30, day 60, and day 90. There will be no follow up visit if the subject has stopped wearing the device. During follow up visits the subjects will be asked about any heart failure related clinical events or change in symptoms that have occurred since the last follow up. The subject will receive a study based weekly phone call asking the subject about any recent heart failure related clinical events or change in heart failure symptoms. During the weekly phone call the subject will be reminded to fill out the daily diary. No phone calls will be given on the week where there is a study follow up visit. There will be no follow up visit if the subject has stopped wearing the device. In case of adverse skin reaction to the μ Cor adhesive and/or electrodes, on the discretion of physician, subjects may discontinue wearing the device for

up to 48 hours. In the event the subject has stopped wearing the device completely, follow up phone calls will continue to be conducted per protocol in order to capture clinical information.

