- 6.2.1.15 The subject's weight will be obtained.
- 6.2.1.16 The subject's previous 90 day hospital admission rate will be determined through chart review.

6.2.2 Visit 2: μ Cor Wear Day 30.

- 6.2.2.1 All subjects will complete the Kansas City HF and study specific questionnaire.
- 6.2.2.2 An in-center appointment will be scheduled to coincide with the end of 60 days of μ Cor wear.
- 6.2.2.3 All subjects will be asked about the following events since their last visit:
 - Any medication changes
 - Any physician visits, both planned and unplanned
 - Any hospitalization, including heart failure hospitalization
 - Any emergency room visits
 - Any symptoms, including syncope, dyspnea, palpitations and chest pain

6.2.2.4 A weight measurement will be obtained.

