Appendix A

Signs/symptoms	0	1	2	3
Dyspnea	None	Seldom	Frequent	Continuous
Orthopnea	None	Seldom	Frequent	Continuous
Fatigue	None	Seldom	Frequent	Continuous
Jugular Venous Distension (cm)	≤6	6–9	10–15	≥15
Rales	None	At bases	At bases to 50% way up the posterior lung field	At bases to > 50% way up the posterior lung field
Pedal edema	Absent/trace	Slight	Moderate	Marked

Table 2: Investigator Assessed Congestion Survey

Month 1							
Subject Diary							
Please rate your symptom (0 = Good 10 = Bad)						Yes or No?	
Day	Date	Symptom				Event	
		Shortness of Breath	Fatigue	Cough	Swelling	Hospitalized?	Medication Change?
1							
2							
3							
4							
5							
6							
7							
8							
9							
10							
11							
12							
13							
14							
15							
16							
17							
18							
19							
20							
21							
22							
23							
24							
25							
26							
27							
28							
29							
30							

Table 3: Sample month of subject diary for reported symptoms

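### Palpitations, syncope and chest pain are collected only by recall at roughly monthly visits, with no stated date or grade, so they cannot be matched in time to the μCor rhythm data or supply the timing and severity that endpoint 3.3.3 asks for

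*Combined protocol and SAP*

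**What the plan says.** Section 2.2, objective 2.2.2, seeks correlations between μCor measurements and symptoms. Its wording is "physiologic variables including thoracic impedance, cardiac rhythm, respiration rate,) and patient reported symptoms". Section 3.3 repeats this as endpoint 3.3.2 and adds endpoint 3.3.3: "Frequency, timing, and severity of patient reported symptoms". Neither section lists the symptoms meant.

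Symptoms reach the database by four documented routes:

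- **Daily diary (Appendix A, Table 3).** It has one row per day and 30 rows per month, with the instruction "Please rate your symptom (0 = Good 10 = Bad". The symptom columns are "Shortness of Breath Fatigue Cough Swelling". Section 3.1.1 describes its purpose as having subjects "rate their degree of specific symptoms of heart failure such as shortness of breath and fatigue".
- **Clinic visits (section 6.2).** Visits 2, 3 and 4 include the item "Any symptoms, including syncope, dyspnea, palpitations and chest pain". At Visits 2 and 3 the lead-in is "All subjects will be asked about the following events since their last visit"; Visit 4 states no recall period. No onset date, severity scale or response format is given.
- **Weekly call (sections 3.1.1 and 6.6).** It covers heart failure events, change in heart failure symptoms, general health status and use of health care. No rhythm symptom is named.
- **Questionnaires (section 6.2).** The Kansas City questionnaire and a study-specific one are completed at each visit. The content of neither is reproduced.

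Section 8.3.2 says the secondary endpoints are judged on strength of correlation, and section 8.4 foresees descriptive and qualitative analysis. No matching window or statistic is given.

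**The concern.** The device records the ECG, so rhythm findings are located in time. A rhythm-symptom analysis is most informative when the symptom is located in time too, so that one can ask whether the arrhythmia came before, with or after it. The protocol itself treats palpitations, syncope and chest pain as symptoms worth collecting, yet puts them on the route with the poorest time resolution and no stated grade. The diary, which would give dates and grades, carries only congestion-type symptoms.

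Two things are at stake: the rhythm part of 2.2.2/3.3.2 for these three symptoms, and the timing and severity parts of 3.3.3 for the same three. The loss is hard to repair afterwards, because the date of a palpitation or faint that was not noted when it happened cannot be reliably reconstructed later.

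**Working it through.** The plan states no figure for this endpoint, so there is nothing to reproduce. The check sets what the objectives need against what each route supplies, and counts records and recall lengths.

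**1. Records per symptom over the main wear period**

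- Diary symptoms: 30 rows per month × 3 months = up to 90 dated ratings per symptom, each on a 0 to 10 scale.
- Palpitations, syncope, chest pain: one enquiry at each of Visits 2, 3 and 4 = 3 scheduled enquiries, with no stated scale.
- Ratio: 90 / 3 = 30.

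Optional extended wear (section 3.1.1) adds further monthly visits for those who accept it. It does not change the time resolution.

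**2. Length of recall at each visit**

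Visits may fall up to 5 days either side of the scheduled day (section 6.2).

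- Day 0 to Visit 2: shortest 30 − 5 = 25 days; longest 30 + 5 = 35 days.
- Visit 2 to Visit 3: shortest (60 − 5) − (30 + 5) = 20 days; longest (60 + 5) − (30 − 5) = 40 days.
- Visit 3 to Visit 4: by the same arithmetic, 20 to 40 days, if the Visit 4 question is taken to look back to Visit 3.

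An undated palpitation reported at a visit can therefore be placed only within a span of 20 to 40 days. A diary entry is placed within one day.

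**3. Need against supply**

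| Needed | Four diary symptoms | Palpitations, syncope, chest pain |
|---|---|---|
| Frequency (3.3.3) | Daily | Presence by interval of about a month |
| Timing (3.3.3) | Day | No onset date stated |
| Severity (3.3.3) | 0 to 10 | No grade stated |
| Correlation with rhythm (2.2.2, 3.3.2) | Day by day | By interval of about a month only |

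**4. Subjects who stop wear**

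Sections 3.1.1 and 6.2 cancel clinic visits once wear has stopped. Visits already made still count, and after stopping there is no μCor rhythm left to correlate. What can be lost is the recall for the last partial interval of wear. Section 3.1.1 says calls continue after wear stops, while sections 6.2 and 6.6 say they do not, so it is unclear whether a call could recover that interval.

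**The case against.** The strongest reply is that 2.2.2 can be carried out as written. It names no symptom and does not pair rhythm with rhythm symptoms. Cardiac rhythm can be set against up to 90 daily ratings of each of four symptoms. This stands. A reader might infer that the rhythm-symptom correlation cannot be derived at all; the documents do not support that.

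Second, monthly data are coarse but not empty. With 500 subjects and three intervals there are up to 500 × 3 = 1,500 subject-intervals, and an excess of joint occurrence over what independence predicts could be seen across them. This also stands. A reader might infer that true and chance coincidence look alike in such data, or that the analysis would show little association whatever the truth. Neither follows. The first considers only a subject who has both, and nothing in the documents shows rhythm to be unrelated to dyspnea or fatigue.

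Third, the study-specific questionnaire and the visit eCRF are not shown, Table 3 is captioned as a sample month, and section 6.6 gives the weekly call a general health-status purpose. Dates or grades may therefore be captured somewhere, and it would be wrong to assert that the visit answers are a bare undated yes or no. But the questionnaire and visit form are completed at visits and would still depend on recall over weeks. The call might pick up a rhythm symptom the subject volunteers, but nothing directs the caller to ask for it.

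Finally, this is a descriptive secondary aim of an observational study. That limits the weight of the point but does not remove it, because the remedy is cheap and the data are lost if not recorded at the time.

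**Conclusion.** The concern holds in a limited form. As documented, the three symptoms have 3 recall enquiries of 20 to 40 days each (25 to 35 for the first), against up to 90 daily graded ratings for each diary symptom. They support only a coarse association with rhythm, by intervals of about a month. They cannot be matched in time to the μCor rhythm data, and the documented instruments do not supply their timing and severity for 3.3.3.

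The conclusion rests on two assumptions: that the forms not shown add no contemporaneous record of these symptoms, and that palpitations, syncope and chest pain are the symptoms most directly tied to rhythm. The second is a general clinical judgement that the documents do not state. The primary objective and the safety objective are unaffected. The change should be made, but it is not critical.

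**What to change.** 1. Add columns for palpitations and for lightheadedness or fainting, and preferably chest pain, to the Table 3 diary, on its existing 0 to 10 scale.
2. Add a field to the weekly-call and visit forms for the onset date of each reported episode of these symptoms, and have the call ask about them by name.
3. In section 8, pre-specify the matching window for the rhythm-symptom association for these symptoms (for example, same day) and the statistic. Run this in addition to the correlations with the four existing diary symptoms, not in place of them.
4. State which symptoms 2.2.2, 3.3.2 and 3.3.3 cover. If the diary is not to be changed, limit these items to the diary symptoms by name, and describe any use of the visit symptoms as interval-level only.

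**Cost:** two or three more entries a day on a form subjects already complete, and an extra date field in the eCRF. No new visit or procedure is needed. Subjects already enrolled will lack the new columns, so the time-matched analysis would cover only those who receive the revised diary, and their number should be reported.
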